## 8.4 Study Design

- Randomized controlled trial of RLF-001 50pmol – 150pmol/kg/hr in 3 ascending doses, each administered over a 12 hr IV infusion on consecutive days
- Check vitals two (2) hours after each dose begins for Side effects (See Flow Chart, Figure 2)
- Endpoint outcomes and assessments for survival, Blood O2, organ failure and TNF- $\alpha$

\* MIC = Maximal Intensive Care

**Figure 1** shows a graphical schema of the RLF100-001 protocol study design.

## Figure 2: Protocol RLF-100-001 Study Flow Chart

## 8.5 RLF-100 Treatment Protocol

**Figure 2** shows a graphical flow chart of the RLF100-001 protocol study design.

Note: The “check ABG” prompts in Figure 2 apply to ventilated patients with arterial lines only. These ABGs are to be carried out mid-infusion, at the 6 hour timepoint.

Note: If a determination is made to slow down the infusion rate by 50% - the next infusion would still be applied at the next 24-hour period. (E.g. if infusion was started at 8:00 AM and it runs for 18 hours, the next infusion should still take place at 8:00 AM the following day.) If infusion is halted, patient remains in the study. Physician can dose next day at last well-tolerated dose for a maximum of 3 doses.

## 8.6 Anticipated Risk

Reported adverse events for intravenous aviptadil include hypotension, tachycardia, facial flushing and watery diarrhea. If this were to develop, the infusion would be slowed or stopped until resolved. See Flow Chart (Figure 2 above).

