Dosage, Route of Administration, and Schedule:	Three escalating doses of RLF-100 (Aviptadil): 50, 100, and 150 pmol/kg/hour or placebo administered over 12 hours via IV infusion on successive days. If side effects cannot be managed with ICU protocol, dose reduced or halted.
Statistical Methods:	Primary endpoint (cumulative distribution of the time to respiratory failure resolution) with concurrent survival through Day 28 will be displayed by a lifetable through Day 28 and analyzed using a proportional hazard model analysis containing 4 pre-defined baseline covariates and randomized treatment group (primary) as well as an unstratified log rank test (secondary). Primary endpoint ascertainment requires that recovery from respiratory failure be maintained for at least 7 days without relapse. The cumulative distribution will be constructed through Day 28 with no censoring for death or withdrawal; such patients will be regarded as failures. Other time to event outcomes will be similarly analyzed with the exception of survival which will censor for any withdrawals. NIAID Score will be analyzed by carrying forward any early deaths through Day 28; other ordinal and continuous outcomes will be assessed by mixed model repeated measures through Day 28. The primary analysis will be based on the modified intent-to-treat (mITT) population to be based on all treated patients.

Sample Size Calculation:	For the primary efficacy endpoint, assuming a 40% success percent in the placebo group by Day 28 and a 62% success percent in the RLF-100 group by Day 28, for log rank test with two-sided overall 5% Type I error and 81% power, the sample size to detect a 22% absolute improvement in the percent achieving respiratory failure resolution by Day 28 (from 40% to 62%) is 198 subjects in the primary analysis group (2:1 randomization favoring the RLF-100 group). A 20% absolute advantage in the percent achieving respiratory failure resolution by Day 28 is deemed to be clinically meaningful.
Interim Analyses	An interim look for safety and futility will be conducted once the first 21 randomized subjects complete Day 7. A second interim look for safety, futility, and efficacy will be conducted once the next 81 subjects complete Day 28 but the study will not be prematurely stopped for efficacy.

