## 11.4 Dosing Regimen

The escalating dosing regimen for RLF-100 is shown in Figure 2. Each infusion is planned for 12 hours duration, however, the infusion (either drug or placebo) may be slowed by up to 50% (for an 18-hour total infusion time) at the discretion of the site personnel if side effects cannot be managed to a clinically-acceptable level by the institution's ICU protocol or SOC. Monitoring of vital signs and other safety measurements will be ongoing and decisions relating to dose-reduction or cessation will be based on the evaluation of these parameters.

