## 11.5 Potential Side Effects of Drug Therapy

Signs and symptoms to look for: facial flushing, tachycardia, hypotension, diarrhea. These will be monitored for the duration of the infusion, and for 12 h afterward, by blood pressure and heart telemetry measurements and patient observation. One identified side-effect of Aviptadil infusion is watery diarrhea. As noted above, non-bloody watery diarrhea  $> 3x/day$  requiring additional fluids and electrolyte supplementation is an enrollment exclusion. If watery diarrhea is observed during infusion, the infusion rate should be first reduced by 50% to relieve symptoms. If symptoms persist cease IV infusion.

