## **15.13            Overall Safety Endpoints**

Standard safety analyses are planned. Adverse events will be coded in MedDRA. The incidence, severity, relationship, and worst degree will be assessed with attention paid to AEs occurring during the first three days when infusion is to be administered. The incidence of SAEs and deaths/withdrawals due to treatment will also be assessed. The following additional adverse events are of special interest:

- Diarrhea that leads to treatment discontinuation
- Renal failure
- Bleeding events
- Liver toxicity
- Hypotension/shock.

All safety results will be presented separately for each treatment group. Safety endpoints will include adverse events, vital signs (VS), and relevant clinical chemistries and hematology parameters. Safety and tolerability will be assessed using two-sided Fisher Exact tests to compare RLF-100 vs. Placebo. For each treatment group as well as for the difference, two-sided 95% confidence intervals will be computed for each system organ class and for any preferred terms with >10% incidence for either study treatment.

Mean changes from randomization baseline will be displayed for each serum chemistry and hematology parameter as well as the shift; unpaired t-tests will be used to compare RLF -100 vs. Placebo at designated study times. In addition, paired t-tests will be performed for the change from randomization baseline within each study treatment group.

The safety population will be used for these analyses.

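### The Synopsis and sections 8.6, 11.4 and 11.5 give three conflicting triggers for changing the infusion, so the stop-based diarrhea event in 15.13 depends on the section followed

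*Combined protocol and SAP*

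**What the plan says.** Five places in the combined protocol and SAP deal with side effects during the infusion.

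- **Synopsis, dosage row:** "If side effects cannot be managed with ICU protocol, dose reduced or halted".
- **Section 11.4:** the infusion may be slowed by up to 50% "at the discretion of the site personnel if side effects cannot be managed to a clinically-acceptable level" under the ICU protocol or standard of care. Dose reduction and cessation are left to an evaluation of the monitored parameters, with no threshold.
- **Section 8.6:** "Reported adverse events for intravenous aviptadil include hypotension, tachycardia, facial flushing and watery diarrhea". The next sentence is: "If this were to develop, the infusion would be slowed or stopped until resolved". It then refers to Figure 2.
- **Section 11.5:** "If watery diarrhea is observed during infusion, the infusion rate should be first reduced by 50% to relieve symptoms". If the symptoms persist, the infusion is ended.
- **Section 8.5:** the text sets no trigger. After a halt the patient stays in the study, and "Physician can dose next day at last well-tolerated dose for a maximum of 3 doses".

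Section 15.13 lists among the adverse events of special interest "Diarrhea that leads to treatment discontinuation". It does not say what counts as discontinuation.

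**The concern.** The Synopsis and 11.4 make action conditional on the side effect being unmanageable. Sections 8.6 and 11.5 do not. Two sites treating the same manageable effect can each follow a written section and act differently.

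Three things are at stake. Patients with the same event may be managed differently. The amount of study drug delivered may depend on which section a site reads. And the 15.13 event is defined by what staff do as well as by what happens to the patient, so its count inherits the inconsistency.

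The text is also incomplete on what follows a stop. Section 8.6 ties the stop to resolution of the effect, which suggests that the infusion resumes. Section 8.5 speaks of dosing the next day. The other sections are silent. The written text does not say what applies after a halt in the first infusion, when no earlier level has been given.

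**Working it through.** This is mainly a comparison of texts; a short exposure sum then shows the scale.

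**1. The sections side by side**

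| Section | Trigger in the text | Action | After a stop |
|---|---|---|---|
| Synopsis | Not manageable under ICU protocol | Reduce or halt | Silent |
| 11.4 | Not manageable under ICU protocol or standard of care; site discretion | Slow by up to 50%; reduction or cessation on monitored parameters | Silent |
| 8.6 | A listed effect develops | Slow or stop, no order given | Until resolution; suggests resumption |
| 11.5 | Watery diarrhea is seen | Halve the rate, then end the infusion if it persists | Silent |
| 8.5 | None | Halving and halting are mentioned | May be dosed next day |

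The Synopsis and 11.4 share one trigger, 8.6 has a second and 11.5 a third.

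**2. A test case: watery diarrhea that the ICU can manage**

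- Synopsis and 11.4: the condition for acting is not met, so there is no change.
- 8.6: slow or stop.
- 11.5: halve the rate, and end the infusion if symptoms persist.

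For manageable flushing, tachycardia or hypotension, 11.5 gives no instruction, but 8.6 still conflicts with the Synopsis and 11.4.

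**3. The 15.13 event**

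A patient whose infusion is ended under 11.5 may count. The same patient left unchanged under 11.4 does not. A patient halted on one day and dosed on the next under 8.5 could be classified either way.

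**4. The plan's own figure**

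Section 11.4 gives 18 hours for a slowed infusion. If the rate is halved at hour t and the full dose is delivered, total time is t + (12 − t)/0.5. This is 18 h for t = 6, 22 h for t = 2 and 24 h for t = 0. The 18 hours also follows if 50% refers to time: 12 × 1.5 = 18, a rate cut of 1 − 12/18 = 33%. That is a separate question, and nothing below depends on it.

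**5. Exposure**

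Inputs from the Synopsis: 50, 100 and 150 pmol/kg/hour, 12 hours each. Planned total: 12 × (50 + 100 + 150) = 3,600 pmol/kg.

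Assumptions, none of them from the documents: manageable diarrhea starts at hour h = 2 or h = 6 of the second infusion; where 11.5 is followed, it persists for 2 hours after halving; and the level last tolerated is that of the first infusion.

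- Synopsis or 11.4, no change: 600 + 1,200 + 1,800 = 3,600 (100%).
- 8.6 read as pause, resume and complete, third infusion as planned: 3,600 (100%).
- 11.5 ends the infusion, then next-day dosing under 8.5: 600 + 100h + 2 × 50 + 600 = 1,500 (42%) for h = 2, or 1,900 (53%) for h = 6.
- 11.5 ends the infusion and the permission in 8.5 is not used: 600 + 100h + 2 × 50 = 900 (25%) for h = 2, or 1,300 (36%) for h = 6.

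**The case against.** The strongest reply is Figure 2. Sections 8.4, 8.5, 8.6 and 11.4 all point to it, and it was not visible in the copy reviewed. It may already contain a single algorithm, including what follows a stop or a first-infusion halt. This stands as a limit: one can say only that the written text is silent there, not that the plan has no rule. It does not remove the conflict between sections that state their own conditions in words.

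Much of the text can also be read together. Section 11.5 may be the specific rule for diarrhea, and ending today's infusion under 11.5 is compatible with permitted dosing tomorrow under 8.5. A reader might infer five different rules, or that no site could comply with all of them. The documents do not support that: there are three triggers, 8.5 states none, and silence is not a contrary rule. The opening of the 8.6 sentence could also refer to watery diarrhea alone. Even then the conflict over manageable diarrhea remains.

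A reader might take a first-infusion stop at hour 2 with nothing further (2 × 50 = 100 pmol/kg, 3% of 3,600) as the lower end of exposure. No passage prescribes that outcome. Likewise, no section states outright that a stopped infusion is resumed and completed.

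Finally, a reader might infer a threat to the efficacy conclusion. Section 13.3 adopts a treatment-policy strategy, 11.4 applies to drug and placebo alike, 12.6 records all adverse events, and the 15.13 event is outside the testing hierarchy in 15.1. That the variation falls mainly on the active arm is a reasonable inference from the list in 8.6, but the documents give no rates by arm.

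**Conclusion.** The concern holds as an internal inconsistency, with medium confidence because Figure 2 was not seen. The firm part is the manageability condition, present in the Synopsis and 11.4 and absent from 8.6 and 11.5, together with the undefined term in 15.13. The same manageable diarrhea may or may not lead to a rate cut or stop, and so may or may not be counted.

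Under the timings assumed above, one patient could receive between 25% and 100% of planned exposure depending on the section followed. That range illustrates the scale; it is neither an estimate nor a frequency, and its lower end needs the 8.5 permission to go unused. The effect is on consistent patient management, delivered exposure and one special-interest safety event. Overall diarrhea incidence is still captured, and Type I error is not affected.

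**What to change.** 1. The clinical team should reconcile the Synopsis, 8.5 with Figure 2, 8.6, 11.4 and 11.5 into one algorithm that the other sections cite. It should state the trigger for each named effect, whether a stopped infusion may resume, and what follows a halt in the first infusion. No clinical rule is proposed here.
2. Define discontinuation in 15.13 against that algorithm, and report an infusion halted with later dosing separately from no further study drug.
3. Record rate changes in the eCRF and report the dose actually received by arm.

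The cost is amendment wording, a site memo and one eCRF field. Appendix A, footnote a, already has infusion start and end times recorded; it does not mention rate changes. Section 14.5 describes the look at 81 completed patients as already done, so the new algorithm can reach only patients enrolled after the change. For earlier patients, apply the 15.13 definition from the recorded infusion data and state where rate changes cannot be recovered.

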## 9. SELECTION OF SUBJECTS

## 9.1 Study Population

The trial will be conducted in hospitalized patients with Critical COVID-19 by FDA/NIH criteria (section 6.2.) Subjects must meet all the inclusion and none of the exclusion criteria to be qualified to participate in this study.

## 9.2

### Inclusion Criteria

All patients entered this trial will have the diagnosis of Critical COVID-19 (test positive in past 7 days). Subjects will be observed for a 1 to 24-hour period, during which time all inclusion criteria must be met. If all criteria are met once (not necessarily simultaneously), the patient will be enrolled and randomized to receive the study drug or placebo within 12 hours of the following entry criteria being fulfilled:

- 1) Critical COVID-19 with respiratory failure by NIH/FDA definition requiring either mechanical ventilation, non-invasive ventilation, or high flow rate nasal cannula at minimum 20L flow and 50% FIO2.
- 2) Physician commitment to maximal Standard of Care treatment – as deemed necessary
- 3) Primary cohort: patients with less than 8 days of exposure to mechanical ventilation, non-invasive ventilation, or high flow rate nasal cannula at a minimum of 20L flow and 50% FIO2.

## 9.3

### Exclusion Criteria

- 1) Pregnancy
- 2) Age <18 years
- 3) Mechanical ventilation for more than 7 days in primary cohort.
- 4) Mean Arterial Pressure < 65 mm Hg with use of pressors per ICU protocol
- 5) Irreversible condition (other than COVID-19) with projected fatal course
- 6) ECMO
- 7) Current or recent (within 30 d) enrollment in another investigational trial of anti-IL6 drug or immunomodulator drug
- 8) Active diagnosis of Acquired immune deficiency syndrome.
- 9) Transplant patients currently immunosuppressed.
- 10) Chemotherapy-induced neutropenia (granulocyte count <1000/mm^3).
- 11) Cardiogenic shock; congestive heart failure – NYHA Class 3 or 4.
- 12) Recent myocardial infarction – within last 6 months and current troponin > 0.5
- 13) Anuria (urine output < 50 ml/d) or other signs of multi-organ failure
- 14) Severe liver disease with portal hypertension; Bilirubin ≥4.0
- 15) Recent stroke or head trauma within last 12 months
- 16) Increased intracranial pressure, or other serious neurologic disorder.
- 17) Liquid diarrhea more than 3x/day; defined as more than 3 non-bloody watery stools within a 24-hour period, requiring additional fluid and electrolyte supplementation

## 10.

### RECRUITMENT, CONSENT & ENROLLMENT

#### 10.1

##### Recruitment & Consent Procedures

All admissions to the intensive care unit will be screened for fulfillment of inclusion criteria by the Principal Investigator. Direct patient consent is always preferred if possible, but patients are sometimes unable to give consent in this setting. The PI or PI's designee will seek consent from the patient's responsible party, after explaining the procedure and consent form, approved by all participating sites. It should be noted that one feature of the COVID-19 pandemic is that non-patients are barred from hospital premises. Therefore, informed consent from responsible parties will generally be obtained telephonically and signature will be obtained via an SMS text message or otherwise compliant consent systems (e.g. REDCAP). Consent will be documented by a witnessed, consent form, to be kept on file together with telephonic signature. This does not preclude a site from obtaining consent via paper, if such arrangements can be made, e.g. fax. Should the patient regain ability to consent, consent will be sought accordingly.

#### 10.2

##### Obtaining Informed Consent

Direct patient consent is always preferred if possible, but patients are sometimes unable to give consent in this setting. IRB-approved written informed consent forms (ICF) will be obtained from the responsible

party of all subjects before any protocol-specified procedures are carried out. For entry into the study, all inclusion criteria must be met, and none of the exclusion criteria can be met. All signed ICF forms will be logged and kept in locked research cabinets or other restricted electronic system under the supervision of the local Site PI and available for audit upon request.

## 10.3 Protecting Confidentiality

Any information obtained in this study will be treated as confidential and will be safeguarded. The data will be coded and kept in a secure location. When published, the results of the study will be in a form that does not identify any of the patients. In compliance with federal regulations, the records of the study will be available to representatives of the Food and Drug Administration.

## 10.4 HIPAA Compliance

The study will be compliant with the Health Insurance Portability and Accountability Act (HIPAA), which protects the privacy and security of healthcare information. All personal identifying information (PII) will be securely stored and only accessible to healthcare providers and authorized personnel only.

## 10.5 Standard of Care Support

Supportive treatment in the ICU, including antibiotics, oxygen, mechanical ventilation, blood pressure-supporting medications, and all other standard of care interventions as needed, will be continued, regardless of participation in the study.

## 10.6 Population Bias

For unknown reasons, males are affected by severe COVID-19 symptoms twice (2X) as often as are females. It is likely that the enrollment in this trial will be consistent with that gender difference. There is no evidence to suggest that RLF-100 will be differently tolerated based on race.

## 10.7 Enrollment

The enrollment will be in accordance with a group sequential design. Up to 12 sites will participate.

The sample size for analysis purposes will be 198 patients (132 drug/66 placebo) for the primary analysis.

## 10.8 Randomization Procedures

Randomization will be on a 2:1 basis with a random block size of 3 or 6; a centralized randomization will be used. Subjects will be stratified according to RDR ( $<200$  mmHg,  $\geq 200$  mmHg) and previous anti-viral therapy for COVID-19 (none, any).

Using this method, even if site personnel believe they can tell the difference between clinical reaction to RLF-100 vs. placebo, they have no possibility to guess what the next allocation will be.

## 10.9 Procedure for Maintaining the Blind

Investigational drug will be delivered in identical infusion syringes, labeled by the hospital research pharmacist who is the only unblinded member of the study site. ICU personnel are entirely blinded, as are patients. Even in the event of unintentional unblinding because of differential efficacy of drug and placebo, the randomization scheme prevents staff from knowing the next treatment assignment. Moreover, the primary and declared secondary endpoints are not subject to interpretation by ICU staff.

## 11. TREATMENT OF SUBJECTS

### 11.1 Maximal Standard of Care

All patients entered in the trial receive Maximal Standard of Care treatment and support, including fluids, antibiotics, vasoactive agents, non-invasive or mechanical ventilation, hemodialysis, surgery, and other supportive measures excluding extra-corporeal membrane oxygenation (ECMO). Ventilation methods are:

- Invasive mechanical ventilation includes ventilation associated with an endotracheal or tracheostomy tube. Types of mechanical ventilation with this interface include volume-controlled and pressure-controlled ventilation. Examples are assist-control, pressure control and APRV
- Non-invasive mechanical ventilation includes CPAP, BiPAP, NIPPV (non-invasive positive pressure ventilation)
- Oxygen delivery systems include HFNC, nasal cannula, non-rebreather mask, Airvo, oxygen hood, Oxymizer, simple face mask, and the Venturi mask.

The need for ECMO will be considered a treatment failure on the basis that the lung has been deemed incapable of supporting adequate metabolic function. Decisions regarding the use of intravenous fluids, cardiovascular and respiratory support, and surgical intervention are made by each patient's attending physician and are not dictated by the study protocol. At the completion of the three 12-hour infusions, patients are followed up to 60 days. The schedule of events reflects study plans to follow all patients for up to 60 days even after discharge, but it will not be practical during the Corona Pandemic either to bring patients back for post-discharge visits or to make home visits. Death while on life support vs. death following discharge from mechanical ventilation will be tracked separately. Discharge from mechanical ventilation means that the treating physicians have deemed the patient capable of breathing without the need for mechanical ventilation. A death that occurs because life support has been withdrawn in the absence of this determination will be recorded as death while on life support.

